11.0 Data Management

Statistical Analysis:

The study design is a non-inferiority study. Primary hemostasis of esophageal variceal bleeding is highly successful (90%), despite rebleeding rates of 10-30%. A superiority trial of primary hemostasis would require a very large number of patients, would require significant resources and would take a long time to recruit.

A non-inferiority trial is appropriate to demonstrate that receiving octreotide for 24 hours is not inferior to the standard of care of 72 hours.

Assuming a primary hemostasis rate of 90% and a non-inferiority margin of 15%, 69 patients will be needed in each group to achieve 90% power. This calculation assumes a type I error rate of 0.05 and equal sample sizes. Anticipating patient drop-out of approximately 15%, a sample size of 80 patients will be required.

Qualitative variables in the two groups will be compared using chi-square test with Yates' correction of Fisher's exact test, when applicable, and represented as percentages. The Mann-Whitney test will be used to compare quantitative variables, which will be expressed as means \pm standard deviations (SD).

Factors associated with re-bleeding and complications will be identified. Logistic regression modeling will be used to assess differences in re-bleeding between the two groups adjusting for significant confounding variables.

All data collected from patients at all sites will be entered in a Redcap project that will be created at MUSC. All sites will have access to this project, however each site will only have viewing and editing rights to the subjects that have been entered by that specific site.

Costs and Payments:

All costs associated with the protocol are part of the routine and standard-of-care for patients with variceal hemorrhage. The researchers, the study patients, or the participating sites will not be remunerated for their participation.

13.0 Provisions to Monitor the Data to Ensure the Safety of Subjects (if applicable)

Data Safety Monitoring Board (DSMB):

After 25, 50, and 75% of the research subjects are enrolled in the study an independent, internal data safety and monitoring board (DSMB) meeting in which we will present accrual and safety data to group members. If the accrual rate is not reached, we will conduct a DSMB meeting at least semi-annually. The DSMB will review any SAEs as they occur. The DSMB will be composed to non-study associated members, specifically: 2 gastroenterologists and 1 statistician at the Lead Investigating Site (MUSC) and it will be responsible for reviewing the data at all sites individually and the data for the study as a whole.

All adverse events including incidences of bleeding in both the control and experimental group will be recorded and submitted to the Institutional Review Board (IRB) within 10 business days. If a serious adverse event occurs, this will be reported to the IRB within 2 business days. The descriptions and definitions of adverse or serious adverse events will be followed and if any adverse events occur, we will report these to the IRB.

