4.0 Study Endpoints (if applicable)

Primary Endpoint:

- Rebleeding within 72-hours after control of hemostasis with EBL

Secondary Endpoints:

- Rebleeding within 7 and 30-days
- Survival within 7 and 30-days
- Complications from octreotide, including, but not limited to: pneumonia, cardiac complications (arrhythmias, heart failure, cardiac ischemia), paralytic ileus, hyperglycemia, diarrhea, abdominal pain, nausea

Rebleeding within 72-hours will be defined as any of the following:

- A drop in hemoglobin by more than 20 percentage points from baseline
- Sustained tachycardia above 100 beats per minute, with or without hematochezia or melena
- Transfusion of >2 unites packed red blood cells after EBP
- Recurrence of hematemesis or ongoing melena
- Urgent or emergent need for Transjugular Intrahepatic Portosystemic Shunt (TIPS)." to control suspected rebleeding

Rebleeding after 72-hours will be defined as:

- Any new episode of hematemesis, melena, or hematochezia (with hemodynamic instability)
- Drop in hemoglobin by more than 20 percentage points OR the need for >2 units packed red blood cells
- Need for TIPS or surgery to control suspected bleeding

Patients who rebleed will be treated per hospital standard of care and physician preference. Treatment of rebleeding will be recorded.

Follow-up Endpoints:

Thirty, 60, 90, 180-day, and 1-year follow-up.

Rebleeding after 72-hours will be defined as:

- Any new episode of hematemesis, melena, or hematochezia (with hemodynamic instability)
- Drop in hemoglobin by 20 percentage points OR need for >2 units packed red blood cells
- Need for TIPS or surgery to control suspected bleeding

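### The plan declares non-inferiority but states no analysis that sets 72-hour rebleeding against the 15-point margin, and its sample size is labelled primary hemostasis, not rebleeding

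*Combined protocol and SAP*

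**What the plan says.** Section 4.0 defines the primary endpoint as "Rebleeding within 72-hours after control of hemostasis with EBL". Sections 3.0 and 10.0 place randomisation after endoscopic band ligation (EBL), with the infusion given after successful EBL.

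Section 11.0 (Statistical Analysis) declares a non-inferiority design and gives the calculation: "Assuming a primary hemostasis rate of 90% and a non-inferiority margin of 15%, 69 patients will be needed in each group", for 90% power. It adds "This calculation assumes a type I error rate of 0.05 and equal sample sizes", without saying whether the error rate is one- or two-sided, and "Anticipating patient drop-out of approximately 15%, a sample size of 80 patients will be required". Section 6.0 sets a goal of 160 patients in all, so the 80 is per group.

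For analysis, Section 11.0 says "Qualitative variables in the two groups will be compared using chi-square test" (with Yates' correction, or Fisher's exact test), and "Logistic regression modeling will be used to assess differences in re-bleeding between the two groups", adjusted for confounders. It mentions no confidence interval and gives no rule that uses the margin.

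The section uses the term primary hemostasis in two ways. One sentence sets it against rebleeding: "Primary hemostasis of esophageal variceal bleeding is highly successful (90%), despite rebleeding rates of 10-30" (per cent, with no time window). The next treats it as the outcome to be compared between groups: "A superiority trial of primary hemostasis would require a very large number of patients".

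**The concern.** A non-inferiority conclusion needs a bound on how much worse the shorter infusion could be, and that bound must be compared with the margin. A test of no difference does neither. When it is not significant, the data may rule out a 15-point excess, or they may be too sparse to tell. The margin appears only in the sample-size sentence, so a team following the plan would have a p-value for a difference and no stated way to answer the trial's question. Section 14.0 accepts that the shorter infusion may lead to more rebleeding, so the decision rule matters.

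The sample-size wording adds to this. Taken literally, primary hemostasis is settled before randomisation and cannot depend on the assigned duration. No 72-hour rebleeding rate is stated anywhere. The background in Section 2.0 gives a relative risk of rebleeding (0.22), rates of bleeding control combined with survival, and a 2-day versus 5-day comparison without a printed rate. The 72-hour definition in Section 4.0 is also broad: it counts sustained tachycardia with or without visible bleeding, and ongoing melena. The assumed rate therefore needs a basis under that definition.

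**Working it through.** **Inputs.** From Section 11.0: rate 90%, margin 15% (read as 15 percentage points), power 90%, type I error 0.05, equal groups, drop-out 15%. From Section 6.0: 160 in total. Assumed: equal true rates in both groups and the usual normal approximation with unpooled variance.

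**1. The plan's own figure.** n per group = (z_α + z_β)² × 2p(1−p) / d². Because p(1−p) is symmetric, a 90% success rate and a 10% rebleeding rate give the same answer.

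- One-sided 0.05: (1.6449 + 1.2816)² × 0.18 / 0.0225 = 8.564 × 8 = 68.5, so 69. This matches.
- One-sided 0.025: (1.9600 + 1.2816)² × 8 = 84.1, so 85. This does not match.
- Drop-out: 69 × 1.15 = 79.4, so 80; and 2 × 80 = 160. This matches.

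The arithmetic is right for its input, and the error rate actually used was one-sided 0.05.

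**2. The stated tests against the margin.** Take assumed counts of 16/80 rebleeds (24-hour group) and 8/80 (72-hour group).

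- Difference = 0.20 − 0.10 = 10.0 points.
- Yates chi-square = 160 × (|16×72 − 8×64| − 80)² / (24 × 136 × 80 × 80) = 160 × 560² / 20,889,600 = 2.40, p = 0.12. Fisher's exact p = 0.12.
- SE = √(0.20×0.80/80 + 0.10×0.90/80) = 0.0559.
- Upper limit of the two-sided 90% interval = 10.0 + 1.645 × 5.59 = 19.2 points; of the 95% interval, 10.0 + 1.96 × 5.59 = 21.0 points.

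The listed test finds no significant difference, while the interval fails the 15-point margin at either level.

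**3. Power for 72-hour rebleeding.** Power = Φ(0.15 / √(2p(1−p)/n) − z_α), one-sided 0.05:

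| Common rebleeding rate | 69 evaluable per group | 80 evaluable per group |
|---|---|---|
| 5% | 99.2% | 99.7% |
| 10% | 90.2% | 93.5% |
| 15% | 79.5% | 84.4% |
| 20% | 71.2% | 76.6% |
| 30% | 60.9% | 66.5% |

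The highest rate that keeps 90% power solves 2p(1−p) = n × 0.0225 / 8.564. This gives p = 10.1% for n = 69 and 11.9% for n = 80. Exact binomial enumeration of the same interval rule agrees: 0.900 and 0.935 at 10%, 0.617 and 0.670 at 30%. All 80 could plausibly be evaluable, because Section 10.0 keeps every patient in hospital for at least 72 hours. The rows above 10% apply only if the undated 10-30% range holds at 72 hours.

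**4. If a two-sided 95% interval were used.** Power at 10% rebleeding is 84% (69) or 88.5% (80), and 90% power holds up to 8.0% (69) or 9.5% (80).

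**The case against.** The sponsor can fairly reply that the sample size is sound and only its label is loose. An outcome fixed before allocation could not be compared between arms, so the sentence about a superiority trial of primary hemostasis makes sense only if the term meant sustained hemostasis, that is, no rebleeding. On that reading the assumed rate is 10% rebleeding, and 69 per group with 90% power is exactly right. This stands as a possible reading. It is not settled, because the sentence before it sets hemostasis against rebleeding, and no basis for 10% is given on either reading.

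A reader might infer from the 10-30% range that the trial is underpowered. The documents do not support that. The range has no time window, and the plan follows rebleeding to 7 days, 30 days and 1 year. Within one population and one definition, a 72-hour rate cannot exceed a later cumulative rate. The breadth of the 72-hour definition could push the other way, so the direction is unknown.

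The sidedness can be recovered from the 69, so stating it is a clarification. Logistic regression also yields an interval, so it could inform a non-inferiority judgement. The plan, however, states no rule linking any interval to the margin, and an odds ratio is not on the scale of a 15-point difference.

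None of this answers the missing primary analysis, which is the main point.

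**Conclusion.** The plan declares a non-inferiority trial with a 15-point margin and then states only analyses of difference. Followed as written, they cannot establish non-inferiority, and a result that fails the margin by about 4 points (19.2 against 15) could be reported as no significant difference. The counts in that example are assumed; the gap they show is in the text.

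The sample-size wording is a linked, lesser fault. If 90% means freedom from 72-hour rebleeding, 69 per group and 90% power are correct at one-sided 0.05. If it does not, the stated power has no basis for the primary endpoint. Given equal true rates, an absolute margin and one-sided 0.05, 90% power holds up to about 10% rebleeding with 69 evaluable per group, or about 12% with 80. It would be wrong to conclude that the input is certainly mistaken or that the trial is underpowered; the documents show neither.

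**What to change.** 1. State the primary analysis in Section 11.0, for example: *The primary analysis is the difference in the proportion with rebleeding within 72 hours (24-hour minus 72-hour group) with a two-sided 90% confidence interval. Non-inferiority is concluded if the upper limit is below 15 percentage points.* The 90% interval matches the one-sided 0.05 that reproduces 69. Keep the chi-square or Fisher tests and the logistic regression as supportive analyses. If the sponsor prefers a 95% interval, restate power at 10% rebleeding as 84% (69 evaluable) or 88.5% (80).

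2. Rewrite the sample-size paragraph on the primary endpoint, for example: *Rebleeding within 72 hours after EBL is assumed to be [x]% in both groups [basis]. With a margin of 15 percentage points and one-sided 0.05, power is [a]% with 69 and [b]% with 80 evaluable patients per group. We will enrol 80 per group (160 in total).* If 10% was meant, [a] and [b] are 90 and 94.

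The cost is wording, plus finding a basis for the rate. No extra patients are required. The downside is that the stated power may become less favourable, and rewording would not restore it. If the supported rate proved higher and the sponsor chose to hold 90% power, the formula in step 1 of the working gives 98 evaluable per group at 15% rebleeding and 122 at 20%. With the plan's inflation that is 98 × 1.15 = 112.7, so 113 enrolled per group, or 122 × 1.15 = 140.3, so 141, against 80 planned.

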6.0 Number of Subjects

We anticipate enrolling approximately 40 subjects at the local MUSC site, with a goal of 160 patients for the entire study)

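### The trial is sized for non-inferiority with a 15-point margin, but the planned analyses only test for a difference and never use the margin

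*Combined protocol and SAP*

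**What the plan says.** Section 11.0 (Data Management, Statistical Analysis) is explicit about the design: "The study design is a non-inferiority study". It gives the purpose as "A non-inferiority trial is appropriate to demonstrate that receiving octreotide for 24 hours is not inferior to the standard of care of 72 hours".

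The margin appears once, in the sizing: "Assuming a primary hemostasis rate of 90% and a non-inferiority margin of 15%, 69 patients will be needed in each group", for 90% power. The next sentence reads "This calculation assumes a type I error rate of 0.05 and equal sample sizes". After about 15% drop-out the requirement becomes 80. This must mean per group, because Section 6.0 is written "with a goal of 160 patients for the entire study".

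The between-group analyses follow. For categorical data: "Qualitative variables in the two groups will be compared using chi-square test with Yates' correction of Fisher's exact test, when applicable". For quantitative data the test is Mann-Whitney. For the adjusted comparison: "Logistic regression modeling will be used to assess differences in re-bleeding between the two groups adjusting for significant confounding variables".

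The primary endpoint in Section 4.0 is "Rebleeding within 72-hours after control of hemostasis with EBL", a yes/no outcome.

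**The concern.** A chi-square or Fisher test takes equal proportions as its null hypothesis. A non-inferiority test takes a difference at least as large as the margin as its null. A large p value from the first says nothing about the second, because a difference beyond the margin can easily be non-significant in a trial of this size.

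No confidence interval for the risk difference, confidence level or rule for declaring non-inferiority is stated. The logistic model does not fill the gap: as described it yields an odds ratio, and no margin is given on that scale.

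Two inputs to any such rule are also unsettled. The 90% rate and 15% margin are attached to primary hemostasis, while the endpoint is rebleeding. The 0.05 is not labelled one- or two-sided.

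Section 14.0 accepts that the shorter infusion might raise rebleeding, and Section 15.0 expects the results to change practice. The decision rule is therefore central to what the trial can claim.

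**Working it through.** **Inputs.** From Section 11.0: hemostasis rate 0.90 in both groups, margin 0.15 (read as absolute percentage points), power 90%, alpha 0.05, 69 per group. From Sections 6.0 and 11.0: 80 per group after drop-out. My assumption: 90% hemostasis is treated as 10% rebleeding within 72 hours. Section 11.0 also mentions rebleeding of 10-30% without a time window; I use 20% and 30% as further control rates for illustration.

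**1. Reproducing the plan's 69.** n = 2 × 0.9 × 0.1 × (z for alpha + z for power)² / 0.15².
- One-sided 0.05: 0.18 × (1.645 + 1.282)² / 0.0225 = 68.5, so 69. This matches.
- One-sided 0.025: 0.18 × (1.960 + 1.282)² / 0.0225 = 84.1, so 85. This does not match.
- Difference-test formulas for 90% versus 75% give 109 (one-sided), 133 (two-sided) or 146 (two-sided with continuity correction). None matches.

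So the trial is sized for a one-sided 0.05 non-inferiority comparison, and the listed tests address a different hypothesis.

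**2. What the listed test would show.** Take 7/69 (10.1%) on 72 hours. The limits are upper limits of the two-sided 90% Miettinen-Nurminen (score) interval for 24 h minus 72 h.

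| 24 h rebleeds | Difference (points) | Yates p | Upper limit (points) | Margin of 15 met? |
|---|---|---|---|---|
| 10/69 | 4.3 | non-significant | 14.0 | yes |
| 11/69 | 5.8 | 0.448 | 15.7 | no |
| 16/69 | 13.0 | 0.068 | 23.6 | no |

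At 17/69 Yates becomes significant (p = 0.043). All counts from 11 to 16 are non-significant and miss the margin, and the planned test cannot separate them from 10/69, which meets it.

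**3. If non-significance were read as non-inferiority.** Set the true difference exactly at the margin and sum binomial probabilities over all 2×2 tables. The entries are the chance of wrongly passing the 24-hour arm.

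| True 24 h vs 72 h | Yates, n = 69 | Fisher, n = 69 | Score rule, n = 69 | Yates, n = 80 | Fisher, n = 80 | Score rule, n = 80 |
|---|---|---|---|---|---|---|
| 25% vs 10% | 43.9% | 42.4% | 4.8% | 36.1% | 35.2% | 4.8% |
| 35% vs 20% | 57.1% | 55.9% | 4.9% | 50.2% | 50.0% | 5.0% |
| 45% vs 30% | 62.6% | 62.6% | 5.3% | 56.4% | 56.4% | 5.0% |

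A simple Wald 90% interval at 25% vs 10% gives 5.4% (n = 69) and 5.6% (n = 80).

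**4. Why the odds ratio does not substitute.** A 15-point excess is an odds ratio of (0.25/0.75)/(0.10/0.90) = 3.0 at a 10% control rate, (0.35/0.65)/(0.20/0.80) = 2.15 at 20%, and (0.45/0.55)/(0.30/0.70) = 1.91 at 30%. No single odds ratio stands for the margin.

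**The case against.** The strongest reply is that the plan omits a primary non-inferiority analysis rather than prescribing a wrong one. The categorical-variable sentence is generic, nothing names it or the logistic model as primary, and a stated margin may be thought to imply an interval analysis. It is fair that the documents never say a p value above 0.05 will count as non-inferiority. The 35% to 63% rates in step 3 therefore describe a possible misuse, not the plan's own error rate. The two approaches also do not always disagree, as 10/69 against 7/69 shows.

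It is also fair that 10% rebleeding is my mapping of the hemostasis figure, and that the 10-30% range may not refer to 72 hours. Miettinen-Nurminen is one acceptable choice; a pre-specified Wald interval would also close the gap.

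None of this removes the problem. The margin alone fixes neither the endpoint, the sidedness nor the interval method, and the choice matters: at 10% rebleeding and 69 per group, score-rule power is 87.9% at one-sided 0.05 and 78.3% at one-sided 0.025. Left open, the choice could be made after the data are seen. Step 2 needs no misreading of a p value.

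**Conclusion.** The concern holds and should be fixed before analysis. The sample size reproduces as a non-inferiority calculation, but every analysis that reaches the primary endpoint is a comparison for difference, and no supplied text gives an interval or decision rule. Some pages were removed before review; the statistical analysis section was not among them.

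Step 2, the unconditional evidence, uses one illustrative control count. The rates in step 3 hold only if non-significance is taken as non-inferiority. Both steps assume an absolute margin applied to 72-hour rebleeding. The defect itself depends on none of these rates.

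**What to change.** Add a primary analysis to Section 11.0, for example: the difference in the proportion rebleeding within 72 hours (24 h minus 72 h) will be estimated with a two-sided 90% Miettinen-Nurminen confidence interval; non-inferiority will be concluded only if the upper limit is below 15 percentage points (one-sided 0.05).

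The sponsor should confirm:
- **Endpoint and margin.** That the 90% rate and 15-point margin apply to freedom from 72-hour rebleeding, so that 10% rebleeding is assumed.
- **Level.** One-sided 0.05 is the level that reproduces 69. One-sided 0.025 (a 95% interval) needs 85 per group before drop-out; with the score rule its power is 78.3% at 69 and 84.5% at 80.
- **Population.** The primary analysis population and the handling of the anticipated 15% drop-out. A supporting analysis in patients who received their assigned duration would help.

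Keep chi-square and Fisher for baseline and adverse-event tables. Label the logistic model supportive, name its covariates in advance (138 patients at 10-30% rebleeding give 138 × 0.10 to 138 × 0.30, about 14 to 41 events), and report a standardised risk difference if it is to be read against the margin.

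The cost is a few sentences and no new data. At 10% rebleeding in both groups, score-rule power is 87.9% at 69 per group (Wald 90.0%) and 91.5% at 80 (Wald 93.5%). If rebleeding were 20% or 30% in both groups, power at 69 would be about 70% or 61% (Wald 72% or 62%). That shortfall comes from the sizing assumption, not from this change.

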approximately 15 minutes and will consist of questions regarding the patients general health status, cirrhosis related health complications and possible side effects of octreotide.

Collected Data:

Additional data collected from medical records during this study will include:

1. Patient demographics including race and ethnicity
2. Presenting symptoms and physical exam findings
3. Past medical history
4. Laboratory results – complete blood count (CBC), liver function tests, ammonia (if checked per hospital standard of care), hepatitis serologies
5. Imaging findings – liver morphology, patency of portal vein
6. Medications – outpatient and during admission
7. Paracentesis
8. Use of antibiotics
9. Time to endoscopy
10. Endoscopic findings
11. Endoscopic treatment
12. Thirty, 60, 90, 180-day and 1 year follow-up will gather the following information as available:
 - a. Patient alive or not
 - b. Laboratory results – complete blood count (CBC), liver function tests, ammonia (if checked per hospital standard of care), hepatitis serologies
 - c. Medication
 - i. Betablockers
 - ii. Antibiotics
 - d. Rebleeding
 - e. Endoscopic findings and treatment

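### Rebleeding and survival followed to one year have only binary methods planned, with no rule for patients lost to follow-up

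*Combined protocol and SAP*

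**What the plan says.** Section 4.0 (Study Endpoints) names rebleeding and survival at 7 and 30 days as secondary endpoints. It then lists follow-up endpoints, "Thirty, 60, 90, 180-day, and 1-year follow-up", followed by a definition of rebleeding after 72 hours. Section 10.0 (Study Design / Methods) follows patients to one year by chart review and telephone. Its list of data at those visits includes "Patient alive or not" and rebleeding, to be gathered where obtainable. The list names no date of rebleeding, death or last contact.

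The analysis plan is in section 11.0 (Data Management). For categorical outcomes: "Qualitative variables in the two groups will be compared using chi-square test", Yates-corrected, or Fisher's exact test, with results given as percentages. For rebleeding there is also a model: "Logistic regression modeling will be used to assess differences in re-bleeding between the two groups adjusting for significant confounding variables". Drop-out appears once, in the sample size: "Anticipating patient drop-out of approximately 15%, a sample size of 80 patients will be required".

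The plan has no time-to-event method, no denominator rule for lost patients, no missing-data method, and no statement on death before rebleeding. It does not say which test applies to the 60-day to one-year data; chi-square or Fisher follows only from the general rule.

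**The concern.** A percentage rebleeding by one year needs a known status at one year for everyone in the denominator. If some patients are lost, the analyst must either count them as event-free, which lowers the proportion, or drop those with unknown outcome while keeping those who rebled before loss, which raises it. The plan does not choose, so the choice could be made after the data are seen. Logistic regression has the same gap.

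The error carries into the group comparison if loss differs between groups or is related to outcome. The documents neither show nor exclude this. Treatment blinding is not described, and section 15.0 anticipates that the 24-hour group may have a shorter stay.

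**Working it through.** **Inputs from the documents.** 90% primary hemostasis, 15-point margin, 90% power, type I error 0.05, 69 per group, 15% drop-out and 80 patients (section 11.0); 160 in total (section 6.0); rebleeding 10–30% with no time frame (section 11.0).

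**Assumptions.** The documents give no one-year rates. I assume one-year risks, each in the absence of the other event, of 30% rebleeding and 10% death, with constant hazards. A fraction L of patients is lost at a time spread evenly over the year, independently of outcome. L = 15% borrows the plan's only figure.

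**1. The plan's own figure.** n = (1.645 + 1.282)² × 2 × 0.90 × 0.10 / 0.15² = 8.567 × 0.18 / 0.0225 = 68.5, so 69 per group (one-sided 0.05). Then 69 × 1.15 = 79.35, so 80 per group and 160 in total. At 15%, 24 of 160 patients are lost, 12 per group of 80.

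**2. True one-year rebleeding.** Hazards are a = −ln(0.70) = 0.3567 and d = −ln(0.90) = 0.1054, so t = a + d = 0.4620. Cumulative incidence = (a/t)(1 − e^(−t)) = 0.772 × (1 − 0.63) = 0.2856, or 28.6%.

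**3. What simple proportions report.** Mean incidence at the time of loss = (a/t)[1 − (1 − e^(−t))/t] = 0.772 × (1 − 0.8008) = 0.1538. Mean probability of being alive without rebleeding at loss = 0.8008.

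- Lost counted event-free: 0.85 × 0.2856 + 0.15 × 0.1538 = 0.2658, or 26.6%.
- Unknown outcomes excluded: unknown = 0.15 × 0.8008 = 0.1201; 0.2658 / (1 − 0.1201) = 0.3021, or 30.2%.

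**4. Between groups, no true difference.** The same formulas with other values of L:

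| Loss | Lost = event-free | Unknown excluded |
|---|---|---|
| 5% | 27.9% | 29.1% |
| 15% | 26.6% | 30.2% |
| 25% | 25.3% | 31.6% |

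Equal loss gives a difference of 0. With 5% versus 25%, the false gap is 27.9 − 25.3 = 2.6 points or 29.1 − 31.6 = −2.5 points.

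**5. Lower rebleeding.** At 10% rebleeding, 10% death and 15% loss, the true 9.5% is reported as 8.8% or 10.2%, an error of about 0.7 point.

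**6. Survival.** With 30% one-year mortality assumed (hazard 0.3567) and 15% loss, mean survival at loss = 0.30 / 0.3567 = 0.841. Observed deaths = 0.85 × 0.30 + 0.15 × 0.159 = 0.279, or 27.9%. With unknowns excluded: 0.279 / (1 − 0.15 × 0.841) = 0.319, or 31.9%.

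**7. Thirty days.** With 30% rebleeding, 30% death and 15% loss, all at constant hazards over the year, the true 2.85% is reported as 2.83% or 2.87%. If events and loss both cluster early, the error would be larger.

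**8. Death without loss.** With L = 0, step 3 returns the cumulative incidence exactly, so death first does not make the fixed-time proportion wrong. One minus Kaplan-Meier with deaths censored would give 30.0% instead of 28.6%.

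**9. Bounds with no assumption about the lost.** If 20 of 68 observed patients in a group of 80 rebleed (29.4%), the proportion over all 80 lies between 20/80 = 25.0% and 32/80 = 40.0%.

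**The case against.** The strongest reply is that the errors are small and fall on secondary data. With 80 per group and 28.6% rebleeding, the standard error of the difference is √(2 × 0.286 × 0.714 / 80) = 7.1 points, so a 2.5-point false gap is about a third of one standard error, and it needs a loss split that no section suggests. Excluding everyone ever lost, including those who rebled first, gives about 28.4% against 28.6% under random loss. All of this stands. But the plan does not specify that exclusion, and it would discard observed rebleeds.

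Several stronger readings are tempting, and the documents do not support them:

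- That the planned analysis *does* bias the comparison. It can; equal random loss with no true difference gives none.
- That counting patients who die first as not rebleeding is an error. Cumulative incidence counts them the same way. Death matters for interpretation: with equal rebleeding hazards (30%) but death of 40% versus 25%, the rebleeding proportions differ by 2.4 points without any effect on bleeding.
- That 15% is the expected one-year loss. It is stated only for the sample size. Because patients stay in hospital for at least 72 hours, most loss should come later, but that is inference.
- That one-year survival is a planned comparison. Survival is named only at 7 and 30 days; vital status is collected to one year.
- That event timing is lost. Section 10.0 lists data categories and is not a case report form. Section 13.0 requires bleeding events to be recorded and reported. Dates are unlisted, not shown to be absent.

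**Conclusion.** The point holds as a gap in method for the later outcomes. With follow-up to one year, incomplete data foreseen and only binary methods planned, the one-year rebleeding proportion could be off by about 2 points in either direction at 30% rebleeding, and by about 0.7 point at 10%. Bias between groups requires unequal or outcome-related loss; about 2.5 points under the assumed 5% versus 25% split is an illustration, not a forecast. These sizes rest on assumed one-year rates, constant hazards and random loss. The 72-hour primary endpoint, observed in hospital, is little affected, and so are the 30-day results under constant hazards. The change should be made because it is cheap and removes a choice now left open until after the data are seen, not because the main conclusion is at risk.

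**What to change.** In section 11.0:

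- For rebleeding beyond 72 hours, estimate cumulative incidence (Aalen-Johansen) with death as a competing event. Do not simply censor deaths.
- For survival, use Kaplan-Meier estimates.
- Report between-group differences with confidence intervals at 7, 30, 60, 90, 180 days and one year, marking 7 and 30 days as the named secondary endpoints and the rest as follow-up.
- Add a sensitivity analysis for losses. Both estimators assume that loss is unrelated to outcome, so include best- and worst-case bounds as in step 9. Report loss by group.
- State that deaths before rebleeding will be shown beside the rebleeding results.

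In section 10.0, add the dates of rebleeding, death and last contact to the follow-up data. The planned chart reviews and calls can supply them.

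The cost is three date fields, a paragraph of analysis text and slightly more analysis work. Sample size and visits do not change.
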